Most BWL programs have not tailored strategies to reduce caloric intake for BED patients. Though there exists considerable variability across BWL interventions, most BWL programs instruct patients to set low to moderate calorie goals and restrict intake of palatable high-calorie foods.^{71, 72} While strict diets often improve binge eating in the short term (even among patients who are in the normative weight range^{73, 74}) long-term adherence over time is 1) difficult to maintain and 2) could promote the reoccurrence of binge eating if dietary restraint is rigidly applied. A recent systematic review assessing the impact of very low calorie diets on binge eating⁶⁵ found that most interventions reduced binge eating during active treatment⁷⁵⁻⁸³, but a re-occurrence in binge eating after treatment occurred in many (but not all) studies.^{76, 77, 79, 84} BWL, if not tailored for BED, may encourage the use of unsustainable restrictive eating behaviors, reducing the efficacy of this approach.

BWL typically emphasizes reduced caloric intake as the primary method for altering the caloric balance, despite evidence that physical activity can reduce binge eating and encourage weight loss in BED. Because most weight loss in BWL is attributed to reductions in calorie intake rather than increases in physical activity^{85, 86} BWL typically devotes more intervention time to maintaining changes in eating behavior rather than physical activity. However, the few available studies that have specifically evaluated physical activity interventions in BED have found that increases in physical activity can reduce binge eating^{87, 88} and encourage weight loss^{54, 55, 87-89}, suggesting that a stronger emphasis on physical activity for BED may be warranted.⁹⁰⁻⁹⁴

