CBT techniques. We chose to focus on reducing binge episodes during Phase 1 based on data suggesting that early reductions in binge eating impact weight loss outcomes.^{14, 169-171} Sessions 1-3 will provide psychoeducation on the maintenance factors for binge eating episodes, introduce patients to self-monitoring, and start the regular eating interventions, which is a key driver of early reductions in binge eating in CBT.^{142, 172} Patients with BED who consume more frequent meals weigh less, suggesting regular eating might indirectly assist in weight loss.^{173, 174} Regular eating produces a rapid reduction in binge eating episodes and rapid response to treatment is highly predictive of successful treatment outcomes, further supporting a strong focus on reducing binge eating episodes early in treatment.¹⁷⁵⁻¹⁷⁸ Unlike the regular eating interventions typically implemented in CBT, our regular eating intervention will incorporate personalized caloric goal ranges for each meal and snack designed to reduce caloric intake. As described above, regular eating interventions are typically weight neutral, likely because calories previously consumed during binge episodes are distributed over non-binge meals.^{56, 57} We believe that providing explicit calorie goals for each eating episode during the implementation of regular eating can help prevent re-distribution.

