Primary Aim (Efficacy of ABBT). Analyses will be conducted via linear mixed effects models for longitudinal data, which increase power by fully exploiting the strong correlation in treatment outcomes of interests (i.e., primarily, percent weight loss and secondarily, percent binge frequency reduction) across time. Patterned covariance matrices as implemented in SAS/STAT PROC MIXED V9.2 will be used to evaluate between group differences for percent weight loss and percent binge reduction across the study as a whole, and at each assessment post-baseline.²²⁵ Separate variance components will be used to capture therapist and participant-within-therapist variation. The within-subject covariance matrix will be assumed common across study arms, with an exponential variance function to deal with heteroscedasticity and a continuous-time AR(1) correlation matrix to accommodate residual autocorrelation over the unequal-size time intervals between follow-ups. Outcomes at all six time points will be estimated jointly for maximum statistical efficiency in the presence of intermittent missingness and loss to follow-up. The model will include random effects for subject and time (with higher-order effects if needed to capture nonlinear change), and fixed effects for treatment arm, time by treatment interaction, demographic information, and baseline values of weight, dietary intake and physical activity. Time-specific covariate-adjusted contrasts will be used to compare outcome between groups.

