Primary Aim (Efficacy of ABBT). The study's data will consist of repeated assessments over time within randomized individuals within each treatment condition. Therefore, power calculations are dependent on both an expected difference between treatment arms as well as the clustering of the data (repeated observations within an individual with up to six repeated measures per participant within one of the two treatment conditions), resulting in a multilevel model structure. Using the method described by Raudenbush²⁵²⁻²⁵⁴ and implemented with the software Optimal Design, power calculations were made for this multilevel model structure. No results are available which directly compare the effect of ABBT and SBT on weight loss in BED patients. However, effect size can be predicted by deriving effect sizes from trials with elements similar to the proposed study, e.g., percent weight loss comparison between ABBT and SBT from the Mind Your Health II study (effect size at 12 months $d=0.39$) and percent weight loss and binge reduction comparison of CBT vs. SBT ($d=0.625$; 30% difference in binge reduction rates).⁶⁴ Based on previous studies, we aim to detect a clinically meaningful difference for both weight and binge eating frequency (3.5% weight loss between groups ($d=0.46$) and a difference in 4 binge eating episodes over the 4-week time period). Baseline covariates that can account for variability in the trial outcomes were taken into consideration in the power analysis. Given these assumptions, a sample size of 104 (52 for each group) is required for 80% power with the significant level of 0.05 and five assessment points, assuming the ratio of the variability of level-1 coefficient to the variability of level-1 residual is one. While allowing for up to 20% attrition, the proposed sample size of 130 is adequately powered to examine a clinically meaningful difference between treatment conditions for both percent weight loss and frequency of binge episodes. We believe this power estimate to be conservative given: 1) attrition estimates are greater than the team has achieved in similar weight control studies; and 2) missing values will be imputed using multiple imputation to maximize the number of the observations used to estimate models.

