Mixed effects models were conducted for Primary Aim 1 (Efficacy of ABT) and Secondary Aim 2 (Between-Subjects Moderation) given nested data within subjects and group. The R “merTools” package was used for models predicting percent weight change and global eating disorder psychopathology change (Knowles et al., 2023), and the R “cplm” package was used for models predicting binge eating frequency change (due to zero-inflated distribution of percent binge eating change at post-treatment and follow-up) (Zhang, 2013). Models for percent weight and binge eating change included fixed effects for the interaction between linear or quadratic time effects and treatment condition (and baseline moderators for Secondary Aim 2). Only linear time effects were included in the models for global eating disorder psychopathology, since the quadratic time fixed effect did not significantly improve model fit. Model selection criteria (e.g., Aikaike information criteria, Bayesian information criteria) and significance testing were used to identify the random effects structure that best fit the model. For percent weight change, models included separate random effects for intercept and slopes of quadratic time effects nested within subjects. For binge eating frequency change, models included random effects for intercept nested within subjects. For global eating disorder psychopathology change, models included separate random effects for intercept and slopes of linear time effects nested within subjects. No differences in results were observed when treatment format delivery (i.e., telehealth vs. in-person groups) was included as a covariate; therefore, results without the inclusion of treatment format delivery as a covariate are reported. Statistically significant interactions were interpreted by plotting simple regression lines for each variable. For all linear mixed effects models, alpha was set at 0.05 and confidence intervals were obtained. Cohen’s f^2 effect size measures were estimated for group x time interaction using methods described by Selya and colleagues (Selya et al., 2012), with $f^2 \geq 0.02$, $f^2 \geq 0.15$, and $f^2 \geq 0.35$ representing small, medium, and large effect sizes, respectively.

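### EDE global is judged by a linear arm-by-time slope over months 0 to 24, which estimates neither the post-treatment nor the follow-up difference between arms

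*SAP*

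**What the plan says.** Protocol C2 places assessments at months 0, 1, 3, 6, 12 (post-treatment) and 24 (one-year follow-up). Protocol C9 makes weight the primary outcome and eating pathology secondary, with EDE global and objective binge frequency as its two main measures.

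The SAP analyses EDE global among its Primary Aim 1 mixed models. For this score, "Only linear time effects were included in the models for global eating disorder psychopathology"; the reason given is that a quadratic term brought no significant gain in fit. The random effects are an intercept and a linear slope per subject. On the treatment effect, "effect size measures were estimated for group x time interaction", and for the linear mixed models "alpha was set at 0.05 and confidence intervals were obtained". Significant interactions are read from plotted regression lines. Percent weight change and binge frequency are treated differently: their models allow linear or quadratic time by arm.

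Protocol C10 (Primary Aim) planned more than a slope: "Time-specific covariate-adjusted contrasts will be used to compare outcome between groups". That sentence is written for percent weight loss and percent binge reduction. For EDE global, the SAP offers by-visit descriptive statistics and mediation models at post-treatment and follow-up, which estimate indirect effects. It names no arm contrast at month 12 or month 24. It also does not state how time is coded or whether a baseline row enters a model for change.

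**The concern.** A constant rate of separation over 24 months is a strong assumption when the intervention stops half-way. The protocol itself leads one to expect uneven change, at least in binge eating. In C6b, "Regular eating produces a rapid reduction in binge eating episodes and rapid response to treatment is highly predictive of successful treatment outcomes". In A5, on very low calorie diets, "a re-occurrence in binge eating after treatment occurred in many (but not all) studies".

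If ABBT gains its advantage early and merely holds it, the arms stop moving apart and the slope sees little. The advantage then goes into the intercept difference, which the SAP does not test as efficacy. A real difference at the end of treatment could be reported as no group-by-time effect.

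**Working it through.** **Inputs.** Visit times 0, 1, 3, 6, 12, 24 (protocol C2). Sample size from protocol C11: "a sample size of 104 (52 for each group) is required for 80% power with the significant level of 0.05 and five assessment points". The documents give no effect size, SD or power figure for EDE global, so I borrow only the 52 per arm. (For weight, d = 0.46 two-sided without covariates needs 150 in total; 104 results from a covariate R² of about 0.30, which is not stated. This has no bearing here.) Assumed for illustration: ABBT benefit D = 0.5 points, between-person SD 0.8, residual SD 0.6, and a random-slope variance of 0 to 0.0004 per month².

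**Leverage.** Mean time = 46/6 = 7.67. Sum of squared deviations = 413.3. Month-24 share = 16.33²/413.3 = 266.8/413.3 = 0.645.

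**Slope difference.** With complete data and a random intercept and slope, the fixed slope equals the least-squares slope: Σ(t − 7.67)·d(t)/413.3, where d(t) is ABBT's lead and positive favours ABBT. Its standard error is √[2(0.36/413.3 + slope variance)/52], which is 0.0058 to 0.0070.

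| Lead at months 0, 1, 3, 6, 12, 24 (fractions of D) | Numerator | Slope per month | z at D = 0.5 |
|---|---|---|---|
| 0, 1, 1, 1, 1, 1 (early, kept) | 7.67 | +0.0186D | 1.3 to 1.6 |
| 0, 1, 1, 1, 1, ½ (early, halved) | −0.50 | −0.0012D | −0.1 |
| 0, 1, 1, 1, 1, 0 (early, gone) | −8.67 | −0.0210D | −1.5 to −1.8 |
| 0, 1/6, ½, 1, 1, ½ (linear to month 6, halved) | 7.39 | +0.0179D | 1.3 to 1.5 |
| 0, 1/12, ¼, ½, 1, 0 (linear to month 12, gone) | 1.78 | +0.0043D | 0.3 to 0.4 |

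**Month-12 contrast, same assumptions.** SD = √(0.64 + 0.36) = 1.0, SE = √(2/52) = 0.196, z = 0.5/0.196 = 2.5. On change from baseline, SD = √0.72 = 0.85 and z is 2.9 to 3.0. These hold in every row, because the month-12 lead is D in each.

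**Power at a reference lead of 0.46 SD** (assumed total SD about 1, ICC 0.5 to 0.6). For an early lead fully kept, the slope test has 19 to 25%. A month-12 contrast has 65% unadjusted, or 77 to 83% if the baseline correlation is 0.5 to 0.6.

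**When the sign reverses.** The break-even share of the month-12 lead remaining at month 24 is minus the numerator from months 1 to 12, divided by 16.33:
- Full from month 1: 8.67/16.33 = 0.53.
- Quick build (0.20, 0.40, then 0.46 SD at months 1, 3 and 6): 4.29/16.33 = 0.26.
- Linear build to month 6: 0.78/16.33 = 0.05.
- Linear build to month 12: no reversal, even if the lead is wholly lost.

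If SBT relapses more, so that the quick-build lead widens from 0.46 to 0.60 SD, the slope is 0.0189 SD per month in ABBT's favour, with 67 to 81% power.

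**Reading month 12 off the fitted lines.** The fitted gap is mean lead + 4.33 × slope. Early and kept: 0.833D + 0.080D = 0.91D. Early and gone: 0.667D − 0.091D = 0.58D. The true gap is D.

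**Coding.** With post-baseline rows only (mean 9.2), an early kept lead is constant and gives a slope difference of exactly 0. With time as visit number 0 to 5 (sum of squares 17.5), early-and-gone gives 0, and early-and-halved gives 1.25/17.5 = 0.071D per visit, or 0.36D over five intervals.

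**The case against.** The strongest answer is the SAP's own model check. A quadratic term was tried and dropped. If both arms shared a marked respond-then-relapse course (say mean changes of 0, −0.5, −0.8, −1.0, −1.0, −0.6 SD), a pooled quadratic test at N = 104 would detect it with about 100% power, and at a quarter of that size with 72 to 81%. Under the illustration above, with SBT flat, it would detect the halved lead with 77% power and the lost lead with 95%. So the reported result is evidence against such courses, and that stands. It does not settle the matter. The SAP does not say that arm-by-quadratic time was tested, and efficacy depends on the shape of the arm difference. An early lead fully kept, with SBT flat, would be flagged only 43% of the time. Nor does an acceptable linear fit turn a 24-month slope into a month-12 effect.

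Timing also matters. ABBT's acceptance-based content starts at session 9, in month 3, so a gradual lead is at least as plausible as one complete at month 1. With a linear build to month 6, halving still leaves the right sign. This limits the reversal claim but not the low power.

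A reader might infer that the protocol predicts a null or reversed result for eating pathology as a whole. It does not. The C6b and A5 passages concern binge episodes, under regular eating and after very low calorie diets, and neither describes EDE global. Relapse within an arm is not loss of the difference between arms, and the protocol's case against standard weight-loss treatment suggests more relapse in SBT. Binge frequency has linear or quadratic time by arm.

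A reader might also infer a departure from plan. C10's contrasts are written for weight and binge reduction, and C10 also asks for differences over the whole study, so no departure is shown for EDE global. By-visit descriptives would show a month-12 gap, but without a test.

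**Conclusion.** The point holds for EDE global only. A group-by-linear-time slope over one treated and one untreated year estimates neither post-treatment efficacy nor maintenance, and the SAP supplies no visit-specific contrast in its place. The firm consequence is weak sensitivity to an early, durable benefit, with z roughly half to two-thirds of that for a simple month-12 contrast. A slope near zero, or of the wrong sign, is possible but needs a lead that is early and substantially lost by month 24; the documents do not show that this is the expected course.

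The figures rest on assumed SDs, complete data, time in months and a baseline row; the last two are unstated in the SAP and change the answer. The primary weight result and binge frequency are untouched. This is a worthwhile improvement to a secondary analysis, not a flaw in the trial's main conclusion.

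**What to change.** For EDE global, fit visit as categorical with treatment-by-visit terms and baseline adjustment; a piecewise line with a knot at month 12 is an acceptable alternative. Report the arm difference with its confidence interval at month 12 as the efficacy result and at month 24 as the maintenance result. Keep the linear slope as a secondary description, and state its time coding, whether a baseline row was included, and whether arm-by-quadratic time was tested.

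The cost is one re-run and a few sentences in the SAP, with no new data. The model carries a few more parameters, so intervals would be slightly wider if the difference really were linear.

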Improving Weight Loss Outcomes for Binge Eating Disorder
Statistical Analysis Plan
NCT03712462
March 18, 2024

Statistical Analysis Plan

Statistical analyses were completed using R software version 4.1.3. Data were imputed via two methods to address missingness. Single imputation was used to impute weight measurements using a return-to-baseline approach, with dropouts assumed to have regained 0.15lb per week up to their baseline weight, consistent with assumptions used by other weight loss clinical trials (Wing et al., 2006). Other missing variables were imputed using R “mice” package (Van Buuren & Groothuis-Oudshoorn, 2011). Descriptive statistics were generated for all variables at each assessment point by treatment condition. There were no differences in age, sex, racial or ethnic status, and therapist credentials between treatment conditions.

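### The retrospective SAP puts a data-selected weight model in place of the protocol's pre-specified one, without explanation and without saying the protocol model was fitted

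*SAP*

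**What the plan says.** The SAP opens in the past tense ("Statistical analyses were completed using R software version 4.1.3") and is dated 18 March 2024; the protocol is dated 26 October 2017. In its mixed-model paragraph the SAP reports three decisions that drew on trial data:

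- Random effects: information criteria and "significance testing were used to identify the random effects structure that best fit the model". The candidate structures and the order of steps are not listed. For percent weight change the outcome was "separate random effects for intercept and slopes of quadratic time effects nested within subjects".
- Time trend for global eating disorder psychopathology, a secondary outcome: linear only, "since the quadratic time fixed effect did not significantly improve model fit".
- Delivery format: "No differences in results were observed when treatment format delivery (i.e., telehealth vs. in-person groups) was included as a covariate". On that ground the SAP presents the model that leaves it out.

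The SAP justifies mixed models "given nested data within subjects and group", but every random effect it names lies within subjects.

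Protocol C10 (Primary Aim) had fixed more. One sentence reads "Separate variance components will be used to capture therapist and participant-within-therapist variation". C10 also specifies the residual variance and correlation structure, baseline covariates and visit-specific adjusted contrasts. Its missing-data section relies on likelihood estimation, with multiple imputation as a sensitivity analysis.

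**The concern.** Within these documents, C10 is the only analysis specification written before the data. A reader of the SAP meets a different primary model, partly chosen from the outcome data, with no account of why the planned parts are absent and no statement that the planned model was run. Two things are at stake. First, the analysis that carries the primary conclusion is no longer the one fixed in advance, so readers cannot see whether the two agree. Second, some omitted parts (clustering, residual autocorrelation, changing variance) determine the standard error of the arm-by-time comparison. If those features are present and left out, the nominal 5% level need not hold.

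**Working it through.** **1. The two specifications for percent weight change, side by side**

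| Element | Protocol C10 | SAP |
|---|---|---|
| Clustering | Variance for therapist and for participant within therapist | Cites group nesting; lists subject-level effects only |
| Residuals | Exponential variance function, continuous-time AR(1) | Not mentioned |
| Random time effects | Subject and time; higher order allowed if needed | Intercept and quadratic slope, chosen by fit and significance |
| Fixed effects | Arm, arm by time, demographics, baseline weight, diet, activity | Arm by linear or quadratic time; no baseline covariate named |
| Comparison | Adjusted contrast at each visit | Group-by-time interaction with f² |
| Missing weights | Likelihood-based; assigning a preset value judged inferior | Single imputation, regain of 0.15 lb per week up to baseline |
| Delivery format | Absent | Checked, then left out |

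Rows one, two and four to six are departures, or omissions that the SAP does not explain. In row three, quadratic time is within what C10 allowed. Row seven is not a departure.

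**2. Link to the sample size.** Protocol C11 gives 104 evaluable and 130 randomised: 104/(1 − 0.20) = 130, reproduced. For d = 0.46, two-sided 5% (two-sided is assumed) and 80% power, n per arm = 2(1.960 + 0.842)²/0.46² = 74.2, so 75 per arm and 150 in total. Multiplying by (1 − R²) for baseline covariates with R² = 0.30 gives 74.2 × 0.70 = 51.9, so 52 per arm and 104. C11 says that covariates were considered but gives no R², so this is one route to 104, not a confirmation of it. It does show that the covariates may have been part of the planned precision.

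**3. What model choice could do to the error rate.** This is a null simulation with 65 per arm, complete data, visits at months 1, 3, 6, 12 and 24, and 1,500 runs. The four candidate random-effects structures were intercept; plus linear; plus quadratic; plus both. All had independent, constant-variance residuals. All covariances are assumed, with time in years.

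- Case A: intercept variance 4, linear-slope variance 9, residual SDs 2, 2.5, 3, 4, 4.5, and residual correlation exp(−Δt/0.6). Total SDs run from 2.8 to 7.8.
- Case B: intercept, linear and quadratic variances 4, 9 and 2.25, with independent residuals of variance 2.25. Total SDs run from 2.5 to 8.8.

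| Rejection at nominal 5% | Joint arm-by-time | 12-month contrast |
|---|---|---|
| A, true covariance fixed in advance (20,000 runs) | 4.7% | 5.0% |
| A, AIC-selected | 10.9% | 8.2% |
| A, intercept + quadratic slope | 11.8% | 13.5% |
| B, AIC-selected | 4.7% | 5.3% |
| B, intercept + quadratic slope | 7.3% | 13.3% |

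BIC selection gave the same figures to within 0.1 point. The Monte Carlo standard error near 5% is √(0.05 × 0.95/1500) = 0.6 points. The intercept + quadratic rows are one reading of the SAP's sentence; if a linear slope was also random, the AIC-selected rows apply. The inflation in Case A comes from leaving out AR(1) and rising variance, not from selection as such: Case B shows none when the truth is among the candidates.

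**4. Clustering.** Protocol C2 gives closed groups of 12–15. With an assumed ICC of 0.01–0.05, the design effect 1 + (m − 1) × ICC runs from 1 + 11 × 0.01 = 1.11 to 1 + 14 × 0.05 = 1.70. If the whole design effect applied and were ignored, the real level would be 2[1 − Φ(1.96/√DE)] = 6.3% to 13.3%, and 104 participants would carry the information of 104/1.11 = 94 down to 104/1.70 = 61. This is a worst case, and it concerns treatment groups rather than therapists.

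**The case against.** Several stronger readings are tempting, and the documents do not support them.

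- *The model was picked because of its treatment result.* The SAP ties random-effects selection to fit and significance testing of the structure, not to the arm effect. Only the delivery-format choice is explicitly tied to results already seen. C10 never included that covariate, and the SAP says the answer was the same either way, so it reads as a disclosed robustness check.
- *Time shape was chosen freely.* C10 allowed higher-order time effects, and the only data-driven time choice described concerns a secondary outcome.
- *A definite error rate follows.* Two to four models with z-statistics correlated 0.8–0.9 would give 7–11% if any significant one were reported. The number of models and the correlation are assumed, the SAP describes no such rule, and at correlation 0.99 the figure falls to 5.7–6.3%.
- *The protocol analysis went unreported.* That can be checked only in these two documents, not in any results publication.

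Other points have weight. The SAP's list of fixed effects may not be exhaustive: it names no treatment main effect either, so silence on covariates and contrasts is not proof of removal. Clinicians are balanced across conditions (C8), so therapist is largely crossed with arm, and omitting it need not distort the arm comparison. C10 is not fully determined: it does not name the demographics, and it models six time points although percent weight change is zero for everyone at baseline. For binge frequency the SAP gives a distributional reason, zero inflation, for leaving the linear model.

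These points limit the size of the problem and shape the remedy. They do not explain why planned parts of the primary model are missing without comment.

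**Conclusion.** The point stands in limited form. By the SAP's own account, the random effects of the primary weight model were chosen from trial data in a document written after analysis. The SAP does not list the therapist components, residual variance and AR(1) structure, baseline covariates or visit-specific contrasts of C10, and it replaces the planned handling of missing weights. It gives no reason, and neither document says that the planned model was fitted.

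The consequence for type I error cannot be sized from the documents. Under the assumed covariances, rejection ranged from 4.7% (no inflation) to 13.5%. The worst-case clustering figures rest on assumed ICCs, and the two sets should not be added. The firm conclusion is about status: the SAP model should not stand as the pre-specified primary analysis while the C10 model is absent.

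**What to change.** For percent weight change, fit the C10 model and report it as the pre-specified primary analysis:

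- keep the therapist and participant-within-therapist components whatever their p-values;
- include the exponential variance function and continuous-time AR(1);
- adjust for baseline weight, dietary intake and physical activity, and for demographics that are now named;
- report adjusted contrasts at each visit;
- handle missing weights by likelihood;
- state how the baseline visit enters, and what was simplified if the full covariance does not converge.

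Show the SAP weight model and the return-to-baseline imputation alongside, labelled post hoc or sensitivity, and list the candidate structures and the order of decisions. A treatment-group random effect is not part of C10; if one is added because the SAP cites group nesting, label it sensitivity.

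Do not force C10's linear model onto binge frequency. Keep the cplm model and label it a post hoc change made for zero inflation. Label the changed mediator windows post hoc too: C10 used changes to months 1 and 3 for outcomes at months 6, 12 and 24; the SAP uses changes to month 3 for post-treatment and to month 6 for follow-up.

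The cost is extra model fitting on data already collected, some effort over convergence, and possibly wider intervals. No new data are needed.
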